13. DATA COLLECTION TOOLS

Have you tested the data collection tool(s) for face validity? Where **more than one tool** is being utilised please fill in the table.

YES, NO

NA (ALL tools are already validated)

Title of DCT	Validated by you? (Y / N / NA - already validated)	Is permission necessary?	Do you have permission? (Supply permission separately)
Demographics and medical history (to be assessed at baseline only).	Y	NA	NA
Miller Behavioural Style Scale (MBSS; to be assessed at baseline only).	NA	Y	Y (see Appendix 11, page 1)

FACULTY OF LIFE SCIENCES AND EDUCATION
FACULTY ETHICS SUB GROUP APPLICATION FORM

The neuroticism scale (10 items; $\alpha = .86$) compiled from the International Personality Item Pool (to be assessed at baseline only).	NA	N	NA
General help seeking questionnaire (GHSQ; to be assessed at baseline and follow-up).	NA	Y	Y (see Appendix 11, page 3)
Health anxiety subscale adapted from The Health Orientation Scale (HOS; to be assessed at baseline and follow-up).	NA	N	NA
Patient-doctor communication will be assessed using the Willingness to Communicate about Health Measure (WTCH; to be assessed at baseline and follow-up).	NA	Y	Y (See Appendix 11, page 4)
The Decision Self-Efficacy Scale (to be assessed at baseline and follow-up).	NA	N	NA
The General Self Efficacy Scale (GSE; to be assessed at baseline and follow-up).	NA	NA	NA
Health Consciousness subscale adapted from The Health Orientation Scale (HOS; to be assessed at baseline and follow-up).	NA	N	NA
Two qualitative items (to be assessed at 2 weeks only) will assess whether research participation has led to improvements in	Y	NA	NA

FACULTY OF LIFE SCIENCES AND EDUCATION
FACULTY ETHICS SUB GROUP APPLICATION FORM

emotional and physical well-being: "Since your engagement in this research, what changes have you noticed in your physical or emotional well-being? "If you have experienced any changes, why do you think these changes occurred?"			
Daily record keeping form (DRK). For participants in the intervention group, they will continually fill out the DRK each day throughout the 2-week research period- whereas the control group will complete this form at baseline and at 2 weeks only.	NA	Y	Y (see Appendix 11, page 5)

PART B

N.B. All questions should be addressed (e.g. provide an answer or state why not applicable).

14. POTENTIAL RISKS AND BURDENS

Describe potential risks and burdens for your participants. Include any potential for distress, discomfort, with an explanation of why it is necessary. For any risk stated here please state what will be done to minimise such effects.

No physical risks from completing this research are anticipated, although participants may be alerted to issues with their physical or mental health through reflecting on their symptoms. Potential participants will be advised on the information sheet (see Appendix 8) that no diagnosis of physical or mental health problems can be made by the research team so that if they are concerned about their physical health or psychological well-being through taking part in the study, they should contact their GP or contact sources of advice and support provided on the information sheet (Appendix 8) and debrief sheets, see Appendix 12, page 1 for debrief sheet presented at the end of the baseline survey, see Appendix 12, page 5 to see the debrief sheet presented at the end of the daily DRK survey, see Appendix 12, page 9 to see the debrief

FACULTY OF LIFE SCIENCES AND EDUCATION FACULTY ETHICS SUB GROUP APPLICATION FORM

sheet presented at the end of the follow-up survey. Should data suggest that the DRK has a negative impact on some individuals, [name]'s supervisors: [name] and [name], will be consulted in the first instance, and a joint decision will be made about the best way to solve the problem, with escalation to the USW research governance officer, [name], if this isn't solved satisfactorily.

Although research participation will not be anonymous, as interested participants will provide their email addresses to the lead researcher via the baseline survey (which will be advertised on www.callforparticipants.com) participants will be assured that their responses to the research materials will be kept entirely confidential. Participants will be made aware that they cannot be identified in any write up, presentation or publication of results of the study. If participants are uncomfortable with sharing such information, they will be reassured that they do not have to take part, and that if they change their mind about their participation, they can close down the survey at any point before submission and any information collected will be deleted or destroyed. This information will be reiterated on the information (**Appendix 8**) and debrief sheets provided at the beginning and end of the research surveys (**see Appendix 12**).

Survey participants will be asked to provide sensitive data (i.e. email addresses, menopausal status, menopausal symptoms, date of last menstrual period), and they will be advised of this via the information sheet (**See Appendix 8**) that sensitive information (and the type of sensitive information) will be asked of them prior to taking part in the study. Participants will be advised that they can withdraw their data from the study at any point up until they receive their £20 Amazon incentive.

To withdraw, participants will be instructed to email [name] with confirmation that they wish to withdraw their data. This information will be included in the information sheet (**Appendix 8**) and repeated in the debrief sheets (**see Appendix 12**). On the consent form (**Appendix 9**) participants will be asked to confirm that they understand they can withdraw their data up until they receive their incentive.

The information sheet will also state that if participants drop out of the study, the information they have submitted up until that point will be retained unless the participant withdraws prior to data analyses. Potential participants will be notified of their rights to withdraw their data, and that data will be retained if they do not give notice of their withdrawal, using this using the following statement:

15. DISCLOSURE OF INFORMATION FROM INTERVIEW/QUESTIONNAIRE

Where research might lead to unexpected disclosure of information by participants that could require notification or other follow up action by the researcher, how will this be handled? This provision should also be explained clearly within the participant information sheet. This must be handled in accordance with the Data Protection Acts 1998 and 2018 (DPA), as well as the new General Data Protection Regulations (GDPR).

This study requires the lead researcher (RA) to contact participants regularly via email. Contact details of interested participants will be provided by www.callforparticipants.com.

FACULTY OF LIFE SCIENCES AND EDUCATION FACULTY ETHICS SUB GROUP APPLICATION FORM

There is a small risk that participants may use this mode of communication to consult [name] for help for physical or mental health problems, or they may disclose information which may require notification or follow up. To mitigate these risks, [name] will use a separate email address ([contact]) from her professional one to contact recruited participants, as agreed with USW IT. All emails sent from this email address will include a note at the end stating the following: *"Please do not reply to this email. If you would like to withdraw, please email [contact]. You can also email [contact] if you would like to opt out of text message reminders. If you have any questions or concerns about this study, please email: [REDACTED]"* It is anticipated that this instruction and the use of a study email address will minimise any chance of instantaneous nuisance replies to [name]. However, please note that [name] has not experienced any negative emails from participants in a recent menopause survey, so this is not anticipated in this study. The study email address will be used to advise recruited participants of their group allocation, their unique username, and provide further instructions (**see Appendix 6**). This email address will also be used to email a link to the DRK intervention to intervention group participants each day of the intervention period (**see Appendix 5 to view DRK link email template**), as well as a link to the follow-up survey to all participants (**see Appendix 6**). [name]'s personal USW email address will be provided on the information sheet (**Appendix 8**) and debrief forms (**see Appendix 12**) should participants have questions about the mechanics of completing the survey, it will be made clear on both forms that participants should only contact [name]'s email address for this purpose. If participants have any questions about anything else related to the survey such as the menopause, or concerns about the study, they will be directed to the Director of Studies ([name]) in the first instance. If participants have concerns or complaints that cannot be answered satisfactorily by [name] on consultation with the wider research team then the issue will be referred to the research governance officer: [name]. These contact details will be provided on the information and debrief sheets. It will also clearly be stated in the information sheet that the research team cannot provide medical advice and that any respondents who are concerned should contact their GP, and examples of help sources are made available to participants on the information and debrief sheets:

It will also be clearly stated in the information sheet that the research team cannot provide medical advice and that any respondents who are concerned should contact their GP.

In terms of complaints about eligibility for claiming the voucher, eligibility criteria will be clearly stated and repeated on the recruitment poster (**see Appendix 7**) presented by www.callforparticipants.com and on social media sites, and the information sheet (**Appendix 8**), minimising the likelihood that participants could state that they didn't know they had to satisfy certain criteria to be eligible for study participation and thus remuneration. Together, these controls should minimise any chance of [name] experiencing negative consequences from any potential issues an individual might have with the research. **See Appendix 13** for the researcher safety protocol, which provides detailed procedures for action, should problems arise. **See Appendix 14** for the risk assessment table, which summarises all potential risks to the research team and participants, including current practices in place to reduce said risks.

17. SCREENING OF IDENTIFIABLE PERSONAL INFORMATION

Give details of the sources (e.g. patient notes) of identifiable personal information that will be used to identify potential participants.

A recruitment poster (**see Appendix 7**) will be hosted on the JISC platform www.callforparticipants.com and social media accounts on Facebook, Twitter and Instagram. This poster will aim to attract potential participants and it will describe the nature of the study, including the eligibility criteria and details of what might be required of participants. The research team will not have direct contact with potential participants, as this will be facilitated by the JISC platform www.callforparticipants.com or verified USW/ KESS social media accounts. Once JISC has identified potential participants from their participant pool (which encompasses individuals who have given permission to be contacted about research participation by researchers), JISC will send these participants the baseline survey which will also encompass screening questions, the information sheet, and consent form. These individuals will be asked to provide their email address on the baseline survey (**see Appendix 1**). Those who complete baseline questionnaires will be emailed by the research team with details of their group allocation and further instruction.

18. ADVERTISEMENTS

All advertising material intended to recruit research participants must be reviewed by the Faculty ethics sub group. This includes but is not limited to: posters, letters, web pages and radio/TV broadcasts.

**FACULTY OF LIFE SCIENCES AND EDUCATION
FACULTY ETHICS SUB GROUP APPLICATION FORM**

Are you intending to use any advertisements? **YES**

If yes, please list the documents appended to this application.

Appendix 7: Online recruitment poster as presented by JISC platform www.callforparticipants.com and social media accounts on Facebook, Twitter and Instagram.

19. APPROACHING PARTICIPANTS

Describe how potential participants will be approached and who will be involved.

In a clinical context, patients should be initially approached by a member of their clinical care team.

Copies of documentation used to approach potential participants should be enclosed with this application, such as a copy of the participant information sheet.

A recruitment poster (**see Appendix 7**) will be hosted on the JISC platform www.callforparticipants.com to attract potential participants and it will describe the nature of the study, including the eligibility criteria and a brief outline of the tasks to be completed. The research team will not have direct contact with potential participants, as this will be facilitated by the JISC platform www.callforparticipants.com. Once JISC has identified potential participants from their participant pool (which encompasses individuals who have given permission to be contacted about research participation by researchers), JISC will send these participants the baseline survey which will also encompass screening questions, the information sheet, and consent form. These individuals will be asked to provide their email address on the baseline survey (**see Appendix 1**). Those who complete baseline questionnaires will be emailed by the research team with details of their group allocation, their unique username, and further instruction (**see Appendix 6 to view instruction email templates**). This study will recruit participants on a rolling basis; therefore, participants will continuously be recruited until the required sample size has been reached. Therefore the 15-day study period will begin once the individual participant has submitted their baseline survey, which will be accessed via the research poster which will be advertised to potential participants from the point of obtaining ethical approval up until the required sample size has been recruited.

Participants who have confirmed their interest by completing the baseline measures and the accompanying consent form will be emailed from the USW email address ([contact]) specific to this study with further instructions. Individuals allocated into the intervention group will be advised that they will be emailed links to complete the DRK each day for 14 days and receive text reminders (should they have opted in to this and provided their mobile number in the baseline survey), those allocated into the control group will be advised that they will be contacted by in 14 days' time, when they will be asked to complete a follow-up questionnaire. **See Appendix 6, page 1 to view intervention group instruction email template, see Appendix 6, page 2 to view control group instruction email template.**

20. INFORMED CONSENT

Describe the arrangements for taking consent from research participants prior to their participation in the research study. Describe the time allowed to decide to take part. Please include a copy of a written consent sheet (where used) with this application.

For consent to be ethical and valid in law participants must be 'capable' of giving consent. Please ensure you have adhered to current guidance on the attributes of a capable person and adhered to such guidance in your recruitment strategy.

The consent form will be included in the baseline survey (view the consent form as it will be presented on the online baseline survey via this link: <https://southwales.onlinesurveys.ac.uk/baseline-questionnaire->

FACULTY OF LIFE SCIENCES AND EDUCATION FACULTY ETHICS SUB GROUP APPLICATION FORM

[preview](#), see Appendix 9 for the consent form only). This consent form will ask participants to confirm that they understand the information sheet provided to them, that they are aware of what the study involves and that they consent to take part in the online study. Participants will be advised to take as long as they wish to decide, with the proviso that data analyses will commence in December 2020, so after this date the survey will be closed.

22. DATA ANALYSIS / STATISTICS

Please describe the arrangements for analysing your data (qualitative and quantitative). Where appropriate discuss what data/statistical analysis will be completed. Where used, please remember to discuss sample size and how the sample size was decided upon.

2 x 2 mixed between-within ANOVA:

The main analysis will include a 2x2 mixed between-within ANOVA to assess differences in symptoms among the symptom monitoring and control groups before and after the 2-week research period. The between-subjects component will encompass the differences in symptoms between the control and intervention groups; the within-subjects variable refers to differences in symptoms before and after the 2-week study period. It is expected that after 2 weeks of symptom monitoring the intervention group will exhibit a greater reduction in symptoms in comparison to the control group (i.e., a significant group x time interaction). As discussed, a power analysis was calculated to identify the minimum sample size needed to detect moderate effects, resulting in the decision to recruit 78 participants, with 39 participants being randomised into each group.

Regressions:

Multiple regressions will explore whether help-seeking intentions as continuous variables as predicted by symptom monitoring group (dummy coded), self-efficacy in patient-doctor communication, self-efficacy in shared decision making, health and symptom awareness, and self-efficacy in goal orientated behaviour, health anxiety, and menopausal symptom changes.

Logistic regressions will establish whether control or intervention group membership (as measured as a dichotomous “Invention/Control” variable) is predicted by health anxiety, variances in emotions and symptoms, help-seeking intentions, self-efficacy in patient-doctor communication, self-efficacy in shared decision making, health and symptom awareness, and self-efficacy in goal orientated behaviour.

Correlations:

FACULTY OF LIFE SCIENCES AND EDUCATION
FACULTY ETHICS SUB GROUP APPLICATION FORM

Correlations will also be computed to assess for associations between certain variables. For example, higher neuroticism X higher negative emotions.

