The primary objective of the proposed study is to experimentally investigate symptom monitoring among menopausal women. The key outcome of interest will be whether daily symptom monitoring influences physical and emotional menopause symptoms, help-seeking, health and symptom awareness, willingness to engage in patient-doctor communication, and perceptions of efficacy in treatment decision-making and goal setting, compared to women who are not asked to monitor their symptoms.

To explore whether daily symptom monitoring can influence physical and emotional menopausal symptoms, this trial will employ the Daily Record Keeping form. The DRK was developed to assess women's daily reactions to IVF treatment (Boivin, 1997; Boivin & Takefman, 1995, 1996) and has since been employed in a number of fertility studies which have charted daily symptom changes (Lancastle, 2006; Ockhuijsen et al., 2014; Bailey et al., 2015). These studies have demonstrated symptom improvements following 2-weeks of using the DRK. The DRK was adapted for the present study to include physical and emotional menopause symptoms, based on the British Menopause Society's index of the most-commonly experienced menopausal symptoms (2016).

Care will be taken when interpreting the results of the DRK, because a number of factors influence symptom reports. For example, individuals who live alone are more likely to report a greater number of physical symptoms and succumb to physical illnesses than those who live with others (Pennebaker, 2012). Likewise, single, unemployed people are more likely to report a greater number of symptoms than individuals in a relationship and employment (Pennebaker, 2012). Because these factors interact with symptom reports, they will be relevant when assessing for covariates during this research (Pennebaker, 2012).

Evidence from the systematic review also indicated that symptom monitoring might induce health-related behavioural changes. Thus, help-seeking intentions will be explored as prior evidence suggests that symptom monitoring can lead to an increased intention to seek medical help (Shafran et al., 2019). Furthermore, difficulties in communicating symptoms can act as a barrier to help-seeking, and findings from the systematic review suggest that symptom monitoring may increase willingness to communicate with health providers (Salaheddin & Mason, 2016; Ismail et al., 2016; Woods et al., 2015). Decision-making

FACULTY OF LIFE SCIENCES AND EDUCATION

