- Investigate whether daily symptom monitoring influences psychological, physical and behavioural health outcomes compared to a non-monitoring control group.
- Assess whether personality and coping style moderate the impact of symptom monitoring on physical or emotional health outcomes during the menopause.

[figure not shown]
FACULTY OF LIFE SCIENCES AND EDUCATION
FACULTY ETHICS SUB GROUP APPLICATION FORM

- Identify whether participants attribute any health improvements to symptom monitoring, or other elements of their research participation.

8. STATEMENT OF STUDY DESIGN (E.g. RCT, Crossover, Cohort studies, Case control, Action research, etc. Max 700 words)

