This study will employ a 2-arm randomised controlled trial, including 1 symptom monitoring intervention group and 1 non-monitoring control group. The main analysis will be a 2 by 2 mixed between/ within-subjects ANOVA. The between-subjects component will compare symptom differences between the symptom monitoring intervention group and the usual care control group. The within-subjects component will compare symptom changes between baseline and after 2-weeks of daily symptom monitoring, and between baseline and after an interval of 2 weeks without monitoring, in the control group. The interaction will establish whether symptom changes differ over time according to whether women are in the symptom monitoring or control group. It is expected that improvements in well-being will occur over time in the symptom monitoring group, in comparison to the control group e.g., positive reactions will increase from baseline, whereas negative reactions will decrease. Symptom reports will be collected using the DRK (Boivin & Takefman, 1995). The intervention group will record their symptoms at baseline and every day for 2-weeks (although only baseline to follow up changes will be subject to analysis), the control group will record their symptoms at baseline and after an interval of 2-weeks with no daily monitoring. The DRK has been used previously in randomised trials of women's reproductive health (e.g., Boivin & Takefman, 1995; Ockhuijsen et al., 2014) to establish the effects of symptom monitoring. This research will take place electronically, questionnaires will be presented to participants in the form of JISC Online Surveys and accompanying information will be attached to emails as Word documents. This study has been designed in this way in response to the ongoing 2020 COVID-19 pandemic. The study admin will be managed by [name] via a dedicated USW email address: [contact].

Research design figure:

All participants:

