interested in receiving text message reminders, participants in the control group will also be sent a reminder text message to complete the follow-up survey.

Hypotheses:

- Symptom monitoring will lead to significant improvements in symptoms after 2 weeks, in comparison to the non-monitoring control group.
- The monitoring group will report increased self-efficacy at follow up in patient-doctor communication, shared decision making, goal orientated behaviour, help-seeking intentions, and heightened health awareness, compared to the control group.
- Women in the intervention group who are monitors according to their scores on the blunting and monitoring scale will report higher negative emotions and physical symptoms than blunters at follow up.
- Greater Health anxiety at follow up will be predicted by symptom changes, demographics (living alone, employment, and marital status), coping style, neuroticism, and symptom monitoring.

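### Hypothesis 2 compares five scales between arms, but section 22 models none of four of them by arm and models help-seeking only with covariate adjustment

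*Combined protocol and SAP*

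**What the plan says.** **What is to be compared.** Section 7 puts these outcomes in the primary objective: "The key outcome of interest will be whether daily symptom monitoring influences physical and emotional menopause symptoms, help-seeking, health and symptom awareness", and the sentence goes on to communication, decision-making and goal setting. The first item in the summary of objectives is to "Investigate whether daily symptom monitoring influences psychological, physical and behavioural health outcomes compared to a non-monitoring control group". The second hypothesis in section 8 says: "The monitoring group will report increased self-efficacy at follow up in patient-doctor communication, shared decision making, goal orientated behaviour"; help-seeking intentions and health awareness complete its list.

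**What is to be analysed.**
- ANOVA. Section 8: "The between-subjects component will compare symptom differences between the symptom monitoring intervention group and the usual care control group". Section 22: "The main analysis will include a 2x2 mixed between-within ANOVA to assess differences in symptoms among the symptom monitoring and control groups". Both name symptoms and nothing else.
- Multiple regression. Section 22: "Multiple regressions will explore whether help-seeking intentions as continuous variables as predicted by symptom monitoring group (dummy coded), self-efficacy in patient-doctor communication". The predictor list continues with decision-making, awareness and goal efficacy, and ends with "health anxiety, and menopausal symptom changes".
- Logistic regression. Section 22: "Logistic regressions will establish whether control or intervention group membership" is predicted by health anxiety, emotions and symptoms, and the five Hypothesis 2 measures.
- Correlations, with one example (neuroticism with negative emotions).

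Section 10 adds only symptom differences by employment, living and relationship status. Section 9 (GHSQ) describes willingness to communicate as the mediator of any effect on help-seeking.

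**The concern.** A hypothesis about a difference between randomised arms needs a model with the scale as outcome and arm as the explanatory factor. WTCH, DSE, GSE and Health Consciousness have none. Allocation is fixed by the random number list, so predicting it from later scores does not estimate what monitoring did to any scale.

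Under joint entry, each logistic coefficient is also conditional on the other outcomes. A benefit shared by several scales is then divided among them, and a scale that did not change can receive a negative coefficient.

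For help-seeking, the arm coefficient is held constant for symptom change, which arises after randomisation, and for communication, the proposed route of the effect. At stake are outcomes that the plan itself places in its primary objective.

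**Working it through.** The plan states no figure on this point, so the first check is a comparison of texts.

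**Step 1. Models by outcome**

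| Hypothesis 2 scale | Outcome in a model with arm as predictor? |
|---|---|
| WTCH, DSE, GSE, Health Consciousness | No (0 of 4); predictors of arm only |
| GHSQ | Yes, with six other variables in the model |

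**Step 2. Direct comparison as reference.** Inputs from section 10: two-sided alpha .05, d = .40, 26 per arm evaluable and 39 per arm recruited. The two-sample noncentral t gives power of 0.293 (26 per arm) and 0.415 (39 per arm) at 0.4 SD, and 0.807 and 0.937 at 0.8 SD. Section 10 states .80 power for 26 per arm, which matches 0.8 SD rather than 0.4 SD. That is a separate matter, but both sizes are shown for this reason.

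**Step 3. Joint logistic model.** Assumptions, none of them in the documents: normal outcomes, common pairwise correlation rho, and seven predictors (emotions and symptoms counted as one). With equal covariance in both arms, the logistic coefficients are the inverse correlation matrix times the vector of effects:

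coefficient for scale j = [effect j − rho × (sum of effects)/(1 + 6 rho)]/(1 − rho)

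- All seven improve by 0.4 (sum 2.8). This reduces to 0.4/(1 + 6 rho), which is 0.25, 0.14 and 0.10 at rho 0.1, 0.3 and 0.5. Entered alone, a scale has coefficient 0.4.
- One scale unaffected, six improve by 0.4 (sum 2.4). At rho 0.1: (−0.24/1.6)/0.9 = −0.17. At 0.3: (−0.72/2.8)/0.7 = −0.37. At 0.5: (−1.2/4)/0.5 = −0.60.

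Simulated Wald tests (2,500 trials per cell; 26 / 39 per arm):

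| rho | All +0.4 SD: power per scale | All +0.8 SD: power per scale | Unaffected scale significantly negative, others +0.4 SD |
|---|---|---|---|
| 0.1 | .117 / .167 | .210 / .345 | .067 / .089 |
| 0.3 | .061 / .078 | .109 / .149 | .200 / .269 |
| 0.5 | .047 / .052 | .069 / .086 | .323 / .462 |
| Reference | .293 / .415 | .807 / .937 | .025 |

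Conditions under which the loss shrinks, at 0.4 SD:
- Single entry: .263 / .401.
- Only one scale improves: .261-.421 / .392-.601 over rho 0 to 0.5.
- Two of the seven outcomes correlated negatively with the other five, rho 0.3: about 16-25%.

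**Step 4. Help-seeking regression.** Assume a true total effect of 0.4 SD and common correlation rho. With six covariates, the expected arm coefficient is 0.4 − [rho/(1 + 5 rho)] × (sum of covariate effects).
- All six are post-randomisation and improve by 0.4 (sum 2.4): 0.4 − 0.0667 × 2.4 = 0.24; 0.4 − 0.12 × 2.4 = 0.11; 0.4 − 0.1429 × 2.4 = 0.06, at rho 0.1, 0.3 and 0.5. The 95% CI then covers 0.4 in 90-91%, 74-81% and 55-70% of simulated trials.
- Only communication and symptoms improve (sum 0.8): 0.35, 0.30 and 0.29.
- Covariates not affected by monitoring, for example baseline scores: 0.40.

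**Step 5. Multiplicity.** Five independent tests at .05: 1 − .95^5 = .226. With health anxiety as a sixth: 1 − .95^6 = .265. Both assume one GHSQ score. The questionnaire rates ten help-source items and the documents define no total.

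**The case against.** Four arguments deserve weight.

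- **Entry is not stated.** Section 22 speaks of logistic regressions in the plural for a single dependent variable, which fits one predictor at a time. On that reading the tests are close to t-tests and almost no power is lost. This stands. What remains is that odds of allocation are reported instead of a mean difference with an interval.
- **The simulated setting is unfavourable.** It needs equal positive correlations and benefit on every outcome, health anxiety included, whereas section 7 raises the possibility that monitoring increases health anxiety. This stands for the size of the harm. With mixed signs, power stays below the direct comparison but well above the lowest figures.
- **The help-seeking model serves a declared aim.** Section 9 poses a mediation question, and arm plus communication is part of such an analysis. This stands. The gap is only that the total effect is not also planned.
- **The study calls itself exploratory** (section 10), and its main analysis is the symptom ANOVA. This limits the severity. It does not supply the missing estimates.

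A reader might infer that Hypothesis 2 will certainly be missed or reversed, or that help-seeking has no arm estimate at all. The documents support neither. They give no correlations, do not state joint or single entry, do not say whether most covariates are baseline, follow-up or change scores, and do include an arm term for help-seeking.

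**Conclusion.** The mismatch between hypothesis and analysis holds on the text alone and needs no assumption. The plan as written yields no between-arm mean difference or confidence interval for four outcomes named in the primary objective. For help-seeking it may not yield the total effect; if the covariates are baseline scores (symptom change cannot be), the arm coefficient comes close to it.

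The further harm is conditional. Under joint entry, positive correlation of 0.1 to 0.5 and a shared benefit of 0.4 SD, power per scale is about 5-17% against 29-41%, and an unaffected scale can appear significantly worse. With single entry, or if one outcome alone improves, the loss is close to nil. The symptom ANOVA is not touched. This should be fixed before analysis, because the open modelling choices could otherwise be settled after the data are seen.

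**What to change.** In section 22:

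1. For GHSQ, WTCH, DSE, GSE and Health Consciousness, regress the follow-up score on arm and baseline score, and report the adjusted mean difference with its 95% CI. Do the same for health anxiety, since sections 7 and 9 also ask whether monitoring influences it. Extending the planned group x time ANOVA to these scales is the minimum.
2. Define the GHSQ score to be used.
3. Report the total effect on help-seeking first. Keep the multi-covariate regression as the mediation or exploratory analysis, stating whether each covariate is a baseline, follow-up or change score.
4. Delete the logistic regressions, or label them exploratory and not evidence for Hypothesis 2.
5. Have the sponsor state the status of these outcomes, which section 7 places in the primary objective, and a multiplicity rule.

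The cost is a few sentences and six simple models. All the scales are already collected at baseline and follow-up. Power at 0.4 SD stays modest: with a baseline to follow-up correlation of .5 to .7, the baseline-adjusted model has .372 to .508 (26 per arm) or .521 to .685 (39 per arm), and group x time has .293 to .447 or .415 to .615. The main gain is a valid, interpretable estimate for each outcome.
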